Acute Oroantral Communication Closure: Resorbable Collagen Membrane vs. Buccal Advancement Flap Outcomes: A Clinical Trial

PCN/0022/KB1/94/20/21

12.02.2021

Study Protocol and Statistical Analysis Plan

Protocol Overview and Rationale

This investigator-initiated, prospective, non-randomized, parallel-group clinical study was designed to compare the clinical effectiveness and early radiographic healing associated with two surgical techniques for closure of acute oroantral communication (OAC) diagnosed within 24 hours after extraction of posterior maxillary teeth. The study was conducted at the Department of Dental Surgery, Faculty of Medical Sciences in Zabrze, Medical University of Silesia. The protocol was approved by the Institutional Review Board (PCN/0022/KB1/94/20/21), and all participants provided written informed consent prior to enrollment.

The study hypothesis was that minimally invasive closure using a resorbable heterogeneous collagen membrane would better preserve soft tissue architecture and reduce postoperative morbidity compared with the conventional Rehrmann buccal advancement flap, while maintaining comparable early bone healing.

Study Population and Enrollment

Consecutive adult patients presenting with acute OAC within 24 hours following extraction of a maxillary posterior tooth were screened for eligibility according to predefined inclusion and exclusion criteria. Twenty-four patients were enrolled; twenty completed the full 90-day follow-up and were included in the final analysis. The mean defect diameter was 3.5 ± 1.0 mm (range 2 to 5 mm), verified clinically and with limited-field CBCT on day 0.

Interventions and Standardization

Participants were assigned to one of two parallel treatment arms based on a predefined clinical protocol and the availability of the membrane technique at the time of treatment. Formal randomization and allocation concealment were not implemented.

All surgical procedures were performed by the same experienced oral surgeon to minimize operator-related variability. Preoperative preparation, socket debridement, smoothing of sharp bony margins, antibiotic prophylaxis, sinus precautions, analgesic recommendations, and follow-up schedules were standardized across both groups.

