Experimental arm: closure using submucosal placement of a resorbable heterogeneous collagen membrane (Creos Xenoprotect) stabilized with horizontal mattress sutures following limited mucoperiosteal elevation without vertical releasing incisions.

Control arm: closure using the classical Rehrmann buccal advancement flap involving trapezoidal full-thickness mucoperiosteal flap elevation with vertical releasing incisions and periosteal releasing incision to permit tension-free coronal advancement.

Follow-up Schedule and Data Collection

Clinical assessments were conducted at baseline (day 0) and on postoperative days 1, 7, 14, and 90. The final radiographic assessment using limited-field CBCT was performed at baseline and at 90 days.

Clinical measurements (vestibular depth, keratinized gingiva width, alveolar socket dimensions) were performed using a calibrated WHO periodontal probe by an independent

examiner blinded to the surgical procedure. Examiner calibration was performed prior to study initiation using repeated measurements in a subset of patients.

Radiographic measurements and region-of-interest (ROI) density analyses were conducted by two trained investigators using standardized protocols in Romexis (v6.4) and ImageJ (v1.53k). Discrepancies were resolved by consensus.

Outcome Measures

Primary endpoint:

- Change in vestibular depth from baseline to 90 days.

Secondary endpoints:

- Change in keratinized gingiva width.
- Change in alveolar socket dimensions.
- Postoperative pain intensity measured with the Visual Analogue Scale (VAS) at days 1, 7, and 14.
- Incidence of postoperative complications (swelling, hematoma, epistaxis, wound dehiscence, persistent communication, fistula formation, clinical sinusitis).
- Normalized bone density at the surgical site derived from CBCT.

Radiographic Density Methodology

Because CBCT gray values are not directly equivalent to absolute Hounsfield Units, density measurements were normalized to adjacent cortical bone within the same scan to reduce inter-individual variability and acquisition-related bias. Regions of interest were placed at three standardized vertical levels of the alveolus (crestal, mid-alveolar, and apical). The arithmetic mean of normalized values was used for statistical analysis.

Statistical Analysis Plan

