All analyses were performed using STATISTICA version 13.0. Continuous variables are presented as mean \pm standard deviation. Categorical variables are presented as counts and proportions.

Assumption testing:

- Normality assessed with the Shapiro–Wilk test.
- Homogeneity of variance assessed with Levene’s test.

Between-group comparisons:

- Independent-samples t test for normally distributed variables with equal variances.
- Mann–Whitney U test when parametric assumptions were violated.

Multiplicity control:

The primary endpoint retained a two-sided alpha of 0.05. Because multiple secondary endpoints were analyzed, Bonferroni correction was applied for secondary comparisons, and these results were interpreted as supportive.

Handling of missing data:

Only participants who completed the 90-day follow-up were included in the final per-protocol analysis. No imputation of missing values was performed.

Power considerations:

Given the final sample size ($n = 20$), the study was adequately sensitive for detecting large between-group differences in soft tissue outcomes but underpowered for moderate radiographic density effects. Therefore, CBCT density findings were prespecified as exploratory.

Bias Control Measures

- Single experienced surgeon to reduce procedural variability.
- Independent blinded clinical assessor.
- Dual-investigator radiographic analysis with consensus resolution.
- Standardized postoperative management in both arms.
- Objective probe-based measurements at predefined time points.

Safety Monitoring

Participants were monitored at each follow-up visit for adverse events, including infection, dehiscence, hematoma, epistaxis, persistent OAC, fistula formation, and signs of maxillary sinusitis. All complications were recorded prospectively. No serious adverse events related to the interventions were reported.

Ethical Considerations

The study complied with the Declaration of Helsinki and applicable institutional requirements. Participation was voluntary, and patients could withdraw at any time without affecting their treatment. Data confidentiality was maintained throughout the study.

Protocol Limitations

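### Closure has no endpoint of its own: failures are two items in a complication list, counted in 90-day completers without an interval, so few or no failures cannot support equal closure

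*Combined protocol and SAP*

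**What the plan says.** Protocol Overview and Rationale describes a study "designed to compare the clinical effectiveness and early radiographic healing associated with two surgical techniques for closure of acute oroantral communication". Its hypothesis concerns soft-tissue preservation, postoperative morbidity and comparable early bone healing.

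Under Outcome Measures, the primary endpoint is "Change in vestibular depth from baseline to 90 days". Closure enters only through one of the five secondary endpoints: "Incidence of postoperative complications (swelling, hematoma, epistaxis, wound dehiscence, persistent communication, fistula formation, clinical sinusitis". Two of those seven items, persistent communication and fistula formation, describe closure failure. No per-patient definition or assessment day is given for them, and the plan does not say whether the items are analysed singly or as any complication. Safety Monitoring has patients checked at each follow-up visit for "adverse events, including infection, dehiscence, hematoma, epistaxis, persistent OAC, fistula formation, and signs of maxillary sinusitis".

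The Statistical Analysis Plan states "Categorical variables are presented as counts and proportions". Under Between-group comparisons it names two tests: "Independent-samples t test for normally distributed variables with equal variances" and "Mann–Whitney U test when parametric assumptions were violated". No test or confidence interval is named for a binary outcome. Handling of missing data limits the final analysis to 90-day completers without imputation. Study Population and Enrollment gives 24 enrolled and 20 analysed. The power note covers soft tissue and radiographic density but not closure.

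**The concern.** A reader of a study comparing two closure techniques will first ask how often each one failed. Under the plan as written, the answer is a count within a complication table, with no statement of its uncertainty and a denominator that leaves out four of the enrolled patients. Failures are likely to be few in a sample this small, so the probable display is zero or one per arm, which is easily read as equally effective closure. The completers-only rule adds to this. Closure failure can show itself at day 1, 7 or 14, and a patient who failed early and then left the study would drop out of the count although the failure had been recorded. A benefit on vestibular depth would then be reported beside a closure result that looks firmer than it is.

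**Working it through.** The documents give no closure rate, margin or sample-size calculation, so there is no figure of theirs to reproduce.

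**Inputs.** From the documents: 24 enrolled, 20 analysed, so 4/24 = 16.7% excluded. Assumed: 10:10 completers, with 8:12 as the range; all 24 enrolled patients were treated; true failure rates of 5%, 10% and 30% are purely illustrative.

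**1. Zero failures in one arm.** The exact (Clopper-Pearson) two-sided 95% upper limit for 0/n is 1 − 0.025^(1/n).
- n = 10: 1 − 0.025^(1/10) = 30.8%
- n = 8: 1 − 0.025^(1/8) = 36.9%
- n = 12: 1 − 0.025^(1/12) = 26.5%

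**2. Zero failures in both arms.** With no events, the Newcombe 95% limits for the difference are minus and plus the Wilson upper limits, z²/(n + z²), with z² = 3.84. For 10:10 this is 3.84/13.84 = 27.8%, so the interval runs from −27.8 to +27.8 points.

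**3. How easily zero failures arises.** The chance of no failure in 20 patients is (1 − p)^20. At p = 10% it is 0.9^20 = 12%; at p = 5% it is 0.95^20 = 36%.

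**4. Ability to see a difference.** Enumerating all 10:10 tables, Fisher's exact test at 0.05 has 5.7% power for 10% v 30%. Significance needs at least 0/10 v 5/10 (p = 0.033).

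**5. The excluded patients.** Their arms, reasons and closure status are not stated. Suppose no completer failed and two patients were lost from each arm of 12. Each arm's rate then runs from 0/12 = 0% (lost patients counted as closed) to 2/12 = 16.7% (counted as failed). For 2/12 the exact 95% interval is 2.1% to 48.4%. If all four were lost from one arm, that arm would run from 0/14 to 4/14 = 28.6%.

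**6. Whether the named tests would give false positives on complications.** Suppose Mann-Whitney were applied to 0/1 data with the tie-corrected normal approximation. Over all common event rates, its true type I error at a nominal 0.05 peaks at 4.2% for 10:10, 5.7% for 9:11 and 5.9% for 8:12. For 0/10 v 4/10 it gives p = 0.029 and Fisher's test gives p = 0.087. With five secondary endpoints as the Bonferroni divisor (the plan does not state one), the threshold is 0.05/5 = 0.01, and neither value passes.

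**The case against.** The plan can be defended on several counts. Its hypothesis makes no claim about closure, and vestibular depth fits the soft-tissue part of that hypothesis. Both closure-failure items are named, are looked for at each visit and are recorded prospectively, so counts by item can be reported as the plan stands. Secondary results are Bonferroni-corrected and called supportive, and Protocol Limitations admits the small sample. Nothing in the documents says that zero failures would be read as equal effectiveness.

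Much of this stands. The primary endpoint need not change, and the misreading is a risk rather than something the plan states. But the stated aim is broader than the hypothesis, the hypothesis-generating caveat covers only bone findings, and recording failures at each visit does not help if the analysis rule then removes the patient.

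A reader might go further and infer that the plan sends complications to Mann-Whitney and so produces false positives. The documents do not support that. The two tests follow normality and variance checks meant for continuous data, and the only rule for categorical data is descriptive. Even if Mann-Whitney were used, its error rate would stay at about 4% to 6%. The gap from Fisher's test mainly reflects that test's conservatism: its true size at 10:10 peaks at 1.3%. What remains is smaller. If complications are tested, the choice of test is open and can matter even at 0.01: 0/10 v 6/10 gives 0.004 by Mann-Whitney and 0.011 by Fisher.

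**Conclusion.** The point holds as a matter of endpoint definition, analysis set and interpretation. Closure failure is not a separately reported outcome, it is planned without an interval, and it is limited to 20 of 24 enrolled patients. At about 10 per arm, zero failures is compatible with a true rate of up to roughly 31% (26% to 37% over arms of 12 to 8), and zero in both arms with a difference of about 28 points either way. No finding on failures at this size can support equal closure. The upper limits depend only on arm size, which is assumed. The power figure also rests on illustrative rates. The effect of the four excluded patients is shown as a range because nothing is known about their status. The point does not show inflated type I error or an unsuitable primary endpoint. It should be addressed, because the change is cheap and protects the conclusion that readers will most want to draw.

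**What to change.** Amend the Outcome Measures and the Statistical Analysis Plan as follows.

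- Define closure failure per patient as persistent communication or fistula at any visit up to day 90, and list it as a separately reported secondary outcome.
- Analyse it in all treated patients instead of completers only. Count failures seen before dropout, state how many patients in each arm have unknown day-90 status, and show the rate with those patients counted as closed and then as failed.
- Give each arm's rate with a Clopper-Pearson 95% interval, and the risk difference with a 95% interval.
- State that no difference in failures does not show equal effectiveness.
- If complications are to be tested, name an exact test in advance and place it within the Bonferroni-corrected secondary family, with the divisor stated.

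The cost is some SAP wording and one small table, drawn from complications already recorded at each visit. The claim about effectiveness becomes more modest. An exact test will have little power at this size, so the intervals should carry the message.

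### The CBCT density endpoint names no time point and no role for day-0 density, so the stated unadjusted tests leave starting density out of a non-randomized comparison of bone healing

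*Combined protocol and SAP*

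**What the plan says.** Under Outcome Measures, density appears as "Normalized bone density at the surgical site derived from CBCT", with no visit and no reference to baseline. In the same list the primary endpoint is "Change in vestibular depth from baseline to 90 days", and two secondary endpoints are "Change in keratinized gingiva width" and "Change in alveolar socket dimensions".

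Radiographic Density Methodology scales each reading against neighbouring cortical bone in the same scan, places regions of interest (ROIs) at three vertical levels of the alveolus, and ends: "The arithmetic mean of normalized values was used for statistical analysis". Follow-up Schedule and Data Collection has "limited-field CBCT was performed at baseline and at 90 days", so a day-0 scan is in the schedule.

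The Statistical Analysis Plan compares groups by an independent-samples t test, or by Mann–Whitney U if assumptions fail. It names no covariate. Its power paragraph labels the density findings exploratory, and Protocol Limitations treats the bone findings as hypothesis-generating.

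**The concern.** The hypothesis in Protocol Overview and Rationale is that the membrane does better on soft tissue and morbidity "while maintaining comparable early bone healing". Healing is what happens between the two scans. Density is the only listed endpoint said to come from CBCT (socket dimensions are taken with a periodontal probe), so the radiographic part of the aim rests on it.

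A comparison of levels speaks to healing only if the arms start alike. Interventions and Standardization says treatment depended on a clinical protocol and on whether the membrane technique was available, without randomization, so the design does not secure equal starting values. Scaling to cortical bone within a scan deals with gray-value calibration. It does not tell the analysis what lay in the ROI on day 0. At stake is whether similar, or different, density in the two arms can be read as similar or different healing.

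**Working it through.** **Inputs from the documents:** CBCT at day 0 and day 90; 20 patients analysed; no randomization; unadjusted two-group tests. The plan states no density mean, SD, correlation or arm sizes, so there is no figure to reproduce.

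**Assumptions:** day-0/day-90 correlation r from 0 to 0.7; day-90-on-day-0 slope b from 0 to 0.7; day-0 arm difference from 0 to 0.10 on the normalized scale; 10 patients per arm.

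**1. Text.** The endpoint bullet gives no time point. The averaging sentence directly follows the one on three ROI levels, so it describes averaging within a scan. No section says which scan or contrast is compared, and none brings day-0 density into the test.

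**2. What a level comparison carries.** Day-90 arm difference = adjusted arm difference + b × (day-0 arm difference).

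| Day-0 arm difference | b = 0 | b = 0.3 | b = 0.7 |
|---|---|---|---|
| 0 | 0 | 0 | 0 |
| 0.10 | 0 | 0.03 | 0.07 |

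**3. Level against gain.** Two invented records, 0.10 to 0.50 and 0.30 to 0.50, share a level of 0.50 but gain 0.40 and 0.20. How often this matters depends on f, the day-0 SD divided by the day-90 SD. The correlation of level with change is (1 − r f) / √(1 + f² − 2 r f):

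- f = 1: 0.59 at r = 0.3 and 0.39 at r = 0.7.
- f = 0.25: 0.97 and 0.98.
- f = 0: exactly 1, so level and change are equivalent.

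**4. Precision.** With equal SDs and the variance of the level set to 1, change has variance 2(1 − r) and the day-0-adjusted outcome has 1 − r².

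| r | Level | Change | Adjusted | Cut by adjustment |
|---|---|---|---|---|
| 0 | 1 | 2.00 | 1.00 | 0% |
| 0.3 | 1 | 1.40 | 0.91 | 9% |
| 0.5 | 1 | 1.00 | 0.75 | 25% |
| 0.7 | 1 | 0.60 | 0.51 | 49% |

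A plain change score is noisier than the level below r = 0.5; the adjusted outcome never has larger residual variance than the level. The adjusted difference does pay for imbalance in the covariate. At 10 per arm its variance is multiplied by 1 + δ²/(0.2 × 18), where δ is the day-0 arm difference in day-0 SDs. A typical chance imbalance is √(2/10) = 0.45 SD, giving 1 + 0.2/3.6 = 1.06. At r = 0, adjustment therefore costs a little precision.

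**5. Chance imbalance is not a second harm.** Chance imbalance moves the level comparison by a typical r × √(2/10) = 0.13, 0.22 and 0.31 SD at r = 0.3, 0.5 and 0.7. Its variance is r² × 0.2, which is the share r² of the sampling variance 0.2 already in the t test's standard error. It is the same quantity as the last column of the table in step 4.

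**6. Change and ANCOVA are different contrasts.** If the records in step 3 were arm means, the level difference would be 0, the change difference 0.40 − 0.20 = 0.20, and the ANCOVA difference with b = 0.5 would be 0 − 0.5 × (0.10 − 0.30) = 0.10. With unequal baselines the plan must say which one it means.

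**The case against.** The strongest reply is that the plan is silent here, not wrong. A reader might infer that the arms are compared on day-90 levels and that day-0 density is never used. The documents do not say so: no time point is given, and a change may have been intended. That stands, and it is why the point concerns an unstated definition and the lack of any baseline term.

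A reader might also infer that density is the one endpoint not written as a change. It is not: VAS pain is a value at days 1, 7 and 14, and complications are an incidence.

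Nor do the documents support a claim that healing differences are in fact hidden. Patients present within 24 hours of extraction and debridement is the same in both arms, so uniformly low day-0 density is plausible, and then level and change nearly coincide. This stands as a limit on size. The documents do not show it to be so, but day-0 density by arm would.

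Finally, density is exploratory, secondary results are only supportive, and the non-random allocation is acknowledged. No confirmatory conclusion depends on this endpoint. That limits the consequence, but an exploratory label does not tell the reader what was compared.

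**Conclusion.** The point holds as an incomplete endpoint definition paired with an analysis that makes no stated use of the patient's starting density, in arms that were not randomized. An arm difference in day-0 density would pass into an unadjusted level comparison by slope times difference: 0 to 0.07 over the assumed ranges, and nil if starting density is uniform or unrelated to day 90. The precision available from the day-0 scan is an r² cut in residual variance, 0% to 49% for r from 0 to 0.7, before a small cost for the covariate. All of these rest on assumed values.

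Two stronger readings fail. Chance imbalance is not a bias on top of the sampling error. The two-fold gap in gain between the invented records is an illustration, not an estimate for this trial. This is a cheap improvement to an exploratory endpoint and does not touch the primary result.

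**What to change.** - Define the endpoint as normalized bone density at day 90, with ROIs at the same three levels on both scans.
- Compare the arms by ANCOVA of day-90 density with the patient's day-0 normalized density as covariate, and report the adjusted difference with its 95% CI.
- Show day-0 density, day-90 density and change by arm, descriptively. This also reveals whether starting density was alike.
- Keep the result exploratory. The plan says it was finalized before database lock, so if this analysis is added after lock, label it post hoc.

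The cost is a few sentences, one analysis, one degree of freedom, and ROI measurement on the day-0 scans if that has not been done. The adjustment does not remove other confounding from non-random allocation, and the report should say so.

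### Pre-tests choose the test for the primary endpoint and send unequal variances to Mann–Whitney; the error rate can drift in either direction, and no effect estimate or confidence interval is specified

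*Combined protocol and SAP*

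**What the plan says.** Under Assumption testing, the Statistical Analysis Plan lists two pre-tests: "Normality assessed with the Shapiro–Wilk test" and "Homogeneity of variance assessed with Levene’s test". Under Between-group comparisons it gives two tests: "Independent-samples t test for normally distributed variables with equal variances" and "Mann–Whitney U test when parametric assumptions were violated". Since the t test is reserved for equal variances, it is read here as the pooled (Student) version. Welch's version is not mentioned.

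The primary endpoint, under Outcome Measures, is "Change in vestibular depth from baseline to 90 days". Under Multiplicity control, "The primary endpoint retained a two-sided alpha of 0.05". No test or model is fixed for this endpoint separately, so the general rule applies to it and to every continuous secondary endpoint.

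On reporting, the plan says "Continuous variables are presented as mean \pm standard deviation". It specifies no estimate of the between-arm difference and no confidence interval.

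On numbers, "Twenty-four patients were enrolled; twenty completed the full 90-day follow-up and were included in the final analysis". Arm sizes are not given. Under Interventions and Standardization, allocation is non-randomized and depends partly on whether the membrane technique was available. The pre-test thresholds, and whether normality is checked per arm, are also not stated.

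**The concern.** A Levene failure alone sends normally distributed data to Mann–Whitney. That test does not correct for unequal spread: when SDs differ, its rejection rate under equal means moves away from the nominal level. When Levene misses a real difference in spread, which is common at this sample size, the pooled t test is kept with a standard error that is wrong unless the arms are equal in size. Neither branch handles unequal variances.

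The two branches also answer different questions, one about means and the other about rank ordering. A Mann–Whitney p value beside means and SDs does not test the contrast on display, and without a specified difference and interval the reader has no planned measure of effect. This part holds whatever the arm sizes are.

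At stake is whether the primary p value keeps its stated 5% level, and what it refers to.

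**Working it through.** **Inputs from the documents.** Two-sided alpha 0.05; 20 patients analysed; the two pre-tests and two tests above. The plan states no effect size, SD or power figure, so there is no calculation of its own to reproduce.

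**Assumed inputs.** Arm sizes 10/10, 8/12 and 6/14; SD ratios 1, 2 and 3; pre-tests at 0.05; Shapiro–Wilk per arm; Levene centred on the mean.

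**Step 1: why the direction depends on which arm is more variable.** The true variance of the mean difference is s1²/n1 + s2²/n2. The pooled t test estimates, on average, [((n1−1)s1² + (n2−1)s2²)/(n1+n2−2)] × (1/n1 + 1/n2). With SDs of 3 and 1:

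- 10/10: true 9/10 + 1/10 = 1.0; pooled (81+9)/18 × 0.2 = 1.0. They agree.
- 6/14, SD 3 in the arm of 6: true 9/6 + 1/14 = 1.571; pooled (45+13)/18 × 0.2381 = 0.767. SE ratio √(0.767/1.571) = 0.70, so the pooled SE is about 30% too small.
- 6/14, SD 3 in the arm of 14: true 1/6 + 9/14 = 0.810; pooled (5+117)/18 × 0.2381 = 1.614. SE ratio √(1.614/0.810) = 1.41, so the pooled SE is about 41% too large.

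**Step 2: simulate the whole rule.** Normal data, equal means, 10,000 trials per row; Monte Carlo SE √(0.05×0.95/10,000) ≈ 0.2 points at 5%. Rule: pooled t if both pre-tests pass, otherwise Mann–Whitney. Type I error in %:

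| Arms | SD ratio, more variable arm | Plan's rule | Mann–Whitney always | Welch always |
|---|---|---|---|---|
| 10/10 | 1 | 4.7 | 4.0 | 4.5 |
| 10/10 | 2 | 5.1 | 5.0 | 4.9 |
| 10/10 | 3 | 6.0 | 6.4 | 5.4 |
| 8/12 | 1 | 5.4 | 5.3 | 5.4 |
| 8/12 | 2, smaller arm | 7.9 | 7.0 | 5.3 |
| 8/12 | 3, smaller arm | 8.7 | 8.8 | 5.2 |
| 8/12 | 2, larger arm | 3.5 | 4.1 | 4.9 |
| 8/12 | 3, larger arm | 3.1 | 3.8 | 4.8 |
| 6/14 | 1 | 5.0 | 4.1 | 5.5 |
| 6/14 | 2, smaller arm | 10.1 | 7.9 | 5.1 |
| 6/14 | 3, smaller arm | 12.0 | 10.6 | 5.6 |
| 6/14 | 2, larger arm | 1.8 | 2.3 | 4.8 |
| 6/14 | 3, larger arm | 1.3 | 1.8 | 4.9 |

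Shorter repeat runs gave the same pattern. The widest departure was 13.7% at 6/14, ratio 3, smaller arm more variable. Centring Levene on the median changed little (8.5% at 8/12 and 12.0% at 6/14, ratio 3).

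**Step 3: where the excess comes from.** At 10 per arm Levene detects a 2:1 SD ratio in only about 41–42% of trials. At 6/14 with ratio 2 in the smaller arm, 51.8% of trials pass both pre-tests, and the pooled t rejects in 15.0% of those. The other 48.2% go to Mann–Whitney, which rejects in 4.8%. Together 0.518×15.0 + 0.482×4.8 = 7.8 + 2.3 = 10.1%. Much of the excess therefore comes from the pooled t surviving a weak gatekeeper, not only from the switch.

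**Step 4: how often the target changes.** With normal data and equal SDs, the pre-tests alone send about 15% of trials to Mann–Whitney. If depth is recorded in whole millimetres with SD 1 mm (an assumption), about 72% go there. With a real effect at 10/10 (equal SDs, difference 1.3 SD), the two tests disagree on significance in 7% of trials.

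**The case against.** Three objections carry weight.

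First, direction. A reader might infer that the error exceeds 5% whenever the arms differ in size and spread. The documents do not support that. It needs the smaller arm to be the more variable one, and neither arm sizes nor SDs are given. The opposite case is at least as easy to argue. The flap arm, with wider elevation and releasing incisions, could plausibly be more variable, and membrane availability could have limited the membrane arm. The rule would then be conservative. That is inference too. What stands is that the level can drift either way.

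Second, size. The double-digit figures need a 6/14 split and a substantial SD ratio. At 10/10 the level is about 5–6%, and at 9/11 with ratio 2 repeat runs gave 5.8% to 6.7%. With equal SDs the level holds at every split tried. This limits how material the error-rate part is, but it does not touch the shifting target or the missing effect estimate.

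Third, a reader might take the rule as leaving the analyst free to pick the better result. It does not: both tests and the condition for switching are written down, and the closing statement under Protocol Limitations says the plan was finalized before database lock and outcome analysis. This is selection by the data under a fixed rule, although the pre-test thresholds are left open.

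**Conclusion.** The concern holds in conditional form. The rule gives normal data with unequal variances a test that does not hold its level for means, and it lets the primary analysis alternate between two targets while the display stays at mean and SD, with no effect estimate or interval specified. That second part rests on the text alone and is the firmest.

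The error-rate part rests on assumed arm sizes, SD ratios of 2 to 3, normal data and pre-tests at 0.05. Across repeat runs, type I error is about 5–6% at 10/10. It is 8–9% (8/12) and 10–14% (6/14) if the smaller arm is more variable, and about 3–4% and 1–2% if the larger arm is. Welch is near 5% in all of these. Nothing in the documents shows that this trial's primary p value is in fact too small or too large. The plan should be changed, but this point alone does not overturn the trial's result.

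**What to change.** Name Welch's t test as the single main unadjusted test for continuous endpoints, with no pre-testing, and report the mean difference with its 95% CI. Keep Mann–Whitney with the Hodges–Lehmann estimate as a named sensitivity analysis that does not replace the main result. State the arm sizes.

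The documents describe enrolment and follow-up as finished. If the outcome analysis has already been done, the prespecified rule should not be silently deleted. Report the Welch result and interval beside the prespecified result and label them as a post hoc change. No new data are needed.

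Cost: with equal variances at 10/10 and a difference of 1.3 SD, power is 78.4% for Welch, 78.9% for the pooled t and 78.0% for the plan's rule. At 10/10 with SD ratio 3 and a difference of 2.9 times the smaller SD, Welch has 74.9% against 71.5% for the rule. At 6/14 with ratio 3 in the smaller arm and a difference of 3.6 times the smaller SD, the rule appears more powerful (79.6% against 65.2%), but there it rejects about 12% of the time with no effect, so the comparison is not like for like.

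Welch is not a full cure. With exponential (strongly skewed) data and SD ratio 3, its error is 8.9% at 10/10 and 11.4% at 6/14, against 15.3% and 19.3% for the plan's rule.
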